5.4. Discontinued Patients

Notification of early patient discontinuation from the study and the reason for discontinuation will be made to the Sponsor (or designee) and will be clearly documented on the appropriate electronic CRF. If a patient is discontinued from the study early, all End of Treatment visit evaluations should be performed at the time of discontinuation, if possible.

Patients who are withdrawn or discontinue early may be replaced at the discretion of the Sponsor.

6. STUDY PROCEDURES

A calendar of study procedures to be conducted for each patient enrolled in the study is presented in a table in Appendix 1, as Appendix 1A (A Cohorts), 1B (B Cohorts), and 1C (C Cohorts), which are also described in the text that follows.

The Investigator must document any deviation from protocol procedures and notify the Sponsor or designee.

Safety and tolerability assessments will include regular monitoring of AEs, changes from baseline in laboratory variables, physical examinations, vital signs, and safety assessments.

From the time that informed consent is obtained through the first administration of investigational drug product, the Investigator must record all SAEs, as well as any non- serious AEs related to protocol mandated procedures, on the adverse event electronic CRF. All other untoward medical occurrences observed during the Screening period, including exacerbation or changes in medical history, are to be captured on the medical history electronic CRF.

6.1. Description of Study Procedures

6.1.1. Patient Enrollment and Treatment Assignment

Patient eligibility will be established at the conclusion of the Screening evaluations. During the dose escalation phase, assignment to dose level will be sequential and as described in Section 5.2 Treatment Plan. For the dose expansion phase, patients will be dosed at the MTD or initial RP2D identified during dose escalation.

6.1.2. Screening Period

Screening procedures shall be performed within 28 days prior to first dose of study drug unless otherwise stated. Procedures may be conducted over multiple visits if necessary.

6.1.3. Informed Consent

Screening begins with the informed consent procedure. The Investigator is obliged to give the patient thorough information about the study and study related assessments, and the patient should be given ample time to consider his or her participation. All patients must sign and date the Institutional Review Board/Independent Ethics Committee (IRB/IEC) approved informed consent form before any study procedures are performed except where noted in the protocol in relation to standard of care procedures. Optional procedures require separate patient consent either within the main or a separate informed consent form, per IRB/IEC requirements.

6.1.4. Disbursement of Study Medication

6.1.4.1. Disbursement of MS-553 Study Medication

Patients will be dispensed the appropriate amount of MS-553. One hundred eighty (180) or 120 of the 100 mg MS-553 tablets in bottles at the 300, or 200 mg BID dose levels, respectively; one hundred twenty (120) 100 mg and sixty (60) 50 mg tablets at the 250 mg BID dose level, an

additional thirty (30) 25 mg tablets will be provided to DS1; one hundred twenty (120) 100 mg and sixty (60) 25 mg tablets at the 225 mg BID dose level (DS2); or sixty (60) 100 mg tablets at the 100 mg BID dose level. Patients will be dispensed the appropriate amount of 25 mg, 50 mg and/or 100 mg tablets of MS-553 based on their assigned dose level or dose adjustments. Additional tablets may be dispensed if necessary in the opinion of the investigator when the subsequent visit will be later than 28 days but within the 3-day window (see Appendix 1A (A Cohorts), 1B (B Cohorts), and 1C (C Cohorts). Refer to the Pharmacy Manual for more specific dispensation details.

6.1.4.2. Disbursement of Acalabrutinib, Venetoclax, and Rituximab

Patients will be dispensed the appropriate amount of acalabrutinib, venetoclax, and rituximab according to the prescribing information located in the package insert. The insurance provider and/or the patient will be responsible for the cost of acalabrutinib, venetoclax, and rituximab.

6.1.5. Instruction to the Patient for Administration

The Investigator must instruct the patient to take the study drug per protocol, the full Prescribing Information, and institutional standard of care for the approved combination drugs. All dosages prescribed and dispensed to the patient and any dose change or interruption must be recorded in the dosage administration record CRF as appropriate. Patients shall be instructed to record their doses in the provided study drug diary. Refer to the Pharmacy Manual for more detailed patient dosing instructions.

6.1.6. Study Drug Accountability and Treatment Compliance

At each clinic visit, patients will be asked to return any remaining study drug from the previous dosing cycle as well as all used and unused study drug containers. The designated site staff will perform accountability as per each clinical site's standard practice.

For MS-553, the study site personnel are to supervise the patients taking study drug at the study site on days in which PK samples are taken. Patients are to keep a study drug diary of the date and time the study drug was taken for doses taken at home. The study drug diaries and used study drug packaging are to be returned to study site personnel at the next study visit. Study site personnel will review the study drug diary, examine the study drug packaging, and document their findings on the appropriate e-CRF. Designated site staff must thoroughly document and re-instruct the patient when significant noncompliance is noted.

For the combination treatments, institutional standard procedures or patient diaries should be used for study drug accountability and treatment compliance recorded.

All records must be readily available for inspection by the Sponsor or its representatives and the U.S. FDA or other regulatory authorities at any time.

6.1.7. Dose Modifications and Dose Delay

Investigators should follow the guidelines described herein for the modification of MS-553 treatment. Any plan to deviate from these guidelines in view of patient safety must be

previously discussed with the study Sponsor and the medical monitor unless there is an urgent need for action.

All dose modifications should be based on the worst preceding toxicity. If study treatment is being held due to toxicity, scheduled visits and all safety assessments in Cycle 1 should continue to occur, even without dispensation of the study drug. Additional scheduled visits and assessments including all PK samplings may be adjusted according to the actual dosing schedule upon the agreement between the investigator, the study medical monitor, and the Sponsor.

Recommended modifications to dosing (not including dose-limiting toxicities in the first cycle) are described in Appendix 2A (MS-553 Recommended Dose Modifications and Delays for Toxicity).

A maximum of three dose reduction steps but not lower than 100 mg BID as a single agent will be allowed, after which the patient will be discontinued from study treatment if there is a need for further dose reduction. In the combination regimens of cohort B and C, dose reductions to not lower than 50 mg BID is allowed.

For patients who undergo dose interruptions (delays) due to toxicity, if the same toxicity returns after re-initiation of treatment, regardless of duration, the second re-initiation of study drug must resume at the next lower dose level. However, the dose of MS-553 that is restarted could be reduced if the investigator feels it prudent to re-challenge at a lower dose. Please refer to Appendix 2A for dose modification instructions.

Recommended modifications to dose and schedule for the combination treatments are outlined in Appendix 2B and 2C, and according to institutional standard of care.

If the patient requires a dose interruption of > 28 days from previous dose for either MS-553 or combination treatment, then the patient must be discontinued from study treatment. Patients who discontinue the treatment due to an adverse event or an abnormal laboratory value, even if not related to study drug, must be followed until resolution or stabilization of the event.

All dose changes or interruptions must be recorded in the dosage administration record CRF.

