APPENDIX 2A: MS-553 RECOMMENDED DOSE MODIFICATIONS AND DOSE DELAYS

[figure not shown]
Worst toxic	ty Grade* (value)		During a cycle of therapy
Hematology	1		
<0.5 x 3	4 neutropenia without 10 ⁹ /L), unless the neu t at the time of study	tropenia was	Hold MS-553 until ANC is ≥ 0.5 x 10 ⁹ /L and until platelets recover to Grade 2 or lower per iwCLL 2018 grading.
and/or	· · · · · · · · · · · · ,	/	If treatment delay is ≤ 7 days, restart at same dose.
	018 Grade 3 or above ocytopenia:		If treatment delay is > 7 days but \leq 28 days, restart at lower dose.
Grade	Decrease in platelets† from ^ baseline value, %		If treatment delay > 28 days, discontinue study treatment
0	No change to 10	-	
1	11-24	-	
2	25-49	-	
3	50-74	-	
4	≥75		
life-thr a resul from b †Platel levels f decrea this wi unless in the i was pr patient	es: 1, mild; 2, moderate eatening; 5, fatal. Deat t of toxicity at any leve aseline will be recorded et counts must be belo for grades 1-4. If, at any se the platelet count is il be considered grade a severe or life-threate nitial platelet count (e. esent at baseline, in wh t is not evaluable for to oble to platelet counts.	h occurring as l of decrease d as grade 5. w normal r level of $<20 \times 10^{9}/L$, 4 toxicity ming decrease g., 20 $\times 10^{9}/L$) hich case the	

Grade 3 Febrile Neutropenia (ANC <1.0 x 10 ⁹ /L with fever)	If ANC at study entry was $\geq 1.0 \times 10^9$ /L:	
	• Hold MS-553 until ANC is $\geq 1.0 \times 10^9/L$	
	If ANC at study entry was < 1.0 x 10 ⁹ /L due to bone marrow involvement:	
	 Hold MS-553 until ANC returns to pretreatment level 	
	If treatment delay is ≤ 7 days, restart at same dose	
	If treatment delay is >7 days but ≤ 28 days, restart at lower dose.	
	If treatment delay >28 days, discontinue study treatment	
Nausea, Vomiting or Diarrhea with maximal prophylaxis		
Grade 3	Hold MS-553 dosing until improved to grade 1 or baseline, then restart at lower dose level for MS-553	
Grade 4	Hold MS-553 dosing until improved to grade 1 or baseline. If improves in <24 hours, restart at lower dose for MS-553	
	If grade 4 GI toxicity persists > 24 hours despite optimal use of SoC, discontinue treatment with MS-553.	
All other Toxicities		

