≥ Grade 3	Hold MS-553 until improved to ≤ Grade 1 or baseline. If treatment delay is < 7 days, restart at same dose or at a lower dose level upon agreement between the investigator and Sponsor. If treatment delay is >7 days but ≤ 28 days, restart at lower dose level. If treatment delay >28 days, discontinue study treatment.	

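### For a repeat hematologic toxicity held 7 days or less, Section 6.1.7 and Appendix 2A give different MS-553 restart doses, and the protocol does not say which text prevails

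*Combined protocol and SAP*

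**What the plan says.** **Section 6.1.7 (Dose Modifications and Dose Delay).** For patients whose dosing was interrupted for toxicity, the rule when the same toxicity comes back after a restart, whatever the duration, is: "the second re-initiation of study drug must resume at the next lower dose level". The next sentence reads: "However, the dose of MS-553 that is restarted could be reduced if the investigator feels it prudent to re-challenge at a lower dose". The paragraph closes with "Please refer to Appendix 2A for dose modification instructions". Earlier in the section, the appendix is introduced with: "Recommended modifications to dosing (not including dose-limiting toxicities in the first cycle) are described in Appendix 2A".

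**Appendix 2A (MS-553).** Restart depends on the type of toxicity and, in most rows, on the length of the delay:

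- The two hematology rows both say: "If treatment delay is ≤ 7 days, restart at same dose". Longer delays, up to 28 days, restart at a lower dose.
- Grade 3 nausea, vomiting or diarrhea: "Hold MS-553 dosing until improved to grade 1 or baseline, then restart at lower dose level for MS-553". Grade 4 events restart lower or lead to discontinuation.
- All other toxicities of Grade 3 or above, when the delay is under 7 days: "restart at same dose or at a lower dose level upon agreement between the investigator and Sponsor". The next band starts above 7 days.

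**Section 7.2** refers sites to Section 6.1.7 and to Appendices 2A, 2B and 2C together, without ranking them.

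**The concern.** Section 6.1.7 turns on whether the event is a recurrence. The hematology rows of Appendix 2A turn on how long the drug was held. A repeat event with a short hold meets both conditions, and the two texts then point to different doses. The reader of Section 6.1.7 is sent to the appendix for instructions, and the appendix, as far as it can be read, does not mention recurrence.

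Two sites could therefore restart the same patient, after the same severe repeat event, at different doses, each following a page of the protocol. The reading also affects the reduction count. Section 6.1.7 allows at most three reduction steps, with floors of 100 mg BID for the single agent and 50 mg BID in the combinations, and a patient who needs more is taken off treatment. A recurrence uses one step under Section 6.1.7 and none under the hematology rows.

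**Working it through.** The protocol states no figure on this point, so the check is a comparison of texts followed by one small calculation.

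**Step 1. Take each row type in Appendix 2A and ask what happens at a second restart for the same toxicity after a short hold.** Section 6.1.7 gives the same answer in every case: the next lower level.

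| Appendix 2A row | Short-hold condition | Restart under Appendix 2A | Against Section 6.1.7 |
|---|---|---|---|
| Grade 4 neutropenia and/or Grade 3+ thrombocytopenia | 7 days or less | Same dose | Differs |
| Grade 3 febrile neutropenia | 7 days or less | Same dose | Differs |
| Grade 3 nausea, vomiting, diarrhea | No 7-day split | Lower level | No conflict |
| Grade 4 nausea, vomiting, diarrhea | Improves in under 24 hours, or persists beyond | Lower dose, or discontinue | No conflict |
| All other Grade 3 or above | Under 7 days | Same or lower, by agreement | Permits but does not require the lower level |

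The count is 2 of 5 row types in flat conflict, 1 of 5 optional against mandatory, and 2 of 5 with no conflict. For delays above 7 and up to 28 days, the hematology and all-other rows already restart lower. Beyond 28 days both texts discontinue. The disagreement is confined to short holds.

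**Step 2. Check the delay bands.** The hematology rows run up to and including 7 days, then above 7 to 28. The all-other row runs below 7 days, then above 7 to 28. A delay of exactly 7 days therefore has a rule in the first case and none in the second.

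**Step 3. Look for text that settles the conflict.** Section 6.1.7 and Section 7.2 both cite the appendix and give no precedence. The sentence after the recurrence rule makes a reduced restart optional and does not say whether it covers the first restart, the second or both. Appendices 2B and 2C, for the partner drugs, do separate first from later occurrences. Appendix 2A, in the text available, does not.

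**Step 4. Size the difference for one patient.** Take a second Grade 4 neutropenia, held 5 days, in a patient at 250 mg BID. Appendix 2A restarts at 250 mg BID. Section 6.1.7 restarts one level down, and the documents contain two candidate ladders:

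- Synopsis list of dose levels (100, 150, 200, 225, 250, 300 mg): next lower is 225 mg; 225/250 = 0.90, so 10% lower.
- Table 2 in Section 3.3.1 (100, 200, 250, 300 mg BID): next lower is 200 mg; 200/250 = 0.80, so 20% lower.

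**Step 5. Number of patients.** This would need the rate at which the same hematologic toxicity recurs after a hold of 7 days or less. The documents give none, so no count can be computed.

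**The case against.** The best defense is that the texts can be read together. Section 6.1.7 is specific to recurrence, is worded as mandatory and applies whatever the duration. Appendix 2A is headed as recommended and gives general bands. On that reading the recurrence rule overlays the table. The optional sentence may concern only a first restart: Section 7.2 pairs the same wording with a return to the prior dose if the toxicity stays away for about four weeks. This reading is plausible, but the protocol does not state it. The duration phrase could mean the hold or the toxicity, and the recurrence paragraph itself ends by handing the reader to the table.

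A second objection is that the appendix reached this review as a broken table with at least one missing figure. That stands as a limit: the absence of a recurrence entry is a statement about the readable text.

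Third, a reader might infer more than the documents support:

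- *That Appendix 2A expressly orders the same dose for a recurrent toxicity.* In the text available it does not mention recurrence. Its rule simply carries no exception.
- *That every short-hold recurrence in about 153 patients is affected.* That figure is planned enrollment, and only two row types conflict flatly.
- *That the primary endpoint is distorted.* It counts events within the DLT periods of Cohorts A1, B1 and C1. In the 28-day windows of A1 and B1 a patient would need a hold, a restart, a recurrence and a second restart. A treatment-related event withholding more than 25% of doses (0.25 × 28 = 7 days' worth) is already a DLT under Section 3.3.5. Appendix 2A also excludes first-cycle DLTs. The four-cycle window of C1 leaves more room, but no effect is shown.
- *That the DS1 and DS2 comparison in Cohort A2 is biased.* No direction or size follows from the documents.

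**Conclusion.** The inconsistency is real and narrow. For a repeat event under either hematology row of Appendix 2A with a hold of 7 days or less, Section 6.1.7 and the appendix prescribe different restart doses, and nothing in the protocol ranks them. For other Grade 3 or higher toxicities the appendix leaves open what Section 6.1.7 requires, and exactly 7 days is unassigned. The gastrointestinal rows do not conflict.

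The size is one dose level per affected restart: 10% to 20% at 250 mg BID, depending on whether 225 mg counts as a level. How often this would occur is unknown. The conclusion rests on the readable text of Appendix 2A containing all its restart rules. It should be corrected because it concerns dosing after severe repeat toxicity and the correction costs little. No effect on the trial's endpoints has been shown. Which rule is clinically right is not judged here.

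**What to change.** Reconcile Section 6.1.7 with Appendix 2A:

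- State one rule for first and recurrent occurrences of the same toxicity in both places, for example by adding an occurrence column to Appendix 2A as in Appendices 2B and 2C.
- Say which text prevails if they differ, and repeat that in Section 7.2.
- Say which restart the optional-reduction sentence in Section 6.1.7 covers, and whether the duration phrase refers to the hold or to the toxicity.
- Name the list of levels that defines one step down.
- Assign a delay of exactly 7 days in the row for all other toxicities.

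The sponsor's clinical team decides the content of the rule. The cost is an edit to one table and a few sentences, with no new data or visits, plus whatever amendment review and site notification the change requires.

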6.1.8. Permitted Concomitant Therapy

In general, the use of any concomitant medication/therapy, including over-the-counter (OTC) medications, deemed necessary for the care of the patient is permitted during the study, with the exception of the prohibited medications noted in Section 5.2.5 and Section 6.1.10.

Hormonal contraceptives are permitted in women of child-bearing potential (see Section 4.2). Hormonal contraceptives include any marketed contraceptive agent that includes an estrogen and/or a progestational agent. It is unknown whether MS-553 could affect the efficacy of hormonal contraceptives and therefore women of childbearing potential on study must agree to use at least two methods of contraception as outlined in the Exclusion Criteria.

The patient must be told to notify the investigator and study personnel about any new medications, including OTC and herbal supplements that he or she begins after the commencement of the study drug. All medications (other than study drug) and significant non-

drug therapies (including physical therapy and blood transfusions) administered during the study must be recorded.

See Section 5.2.4 for additional information on concomitant and supportive therapy, instructions, in particular for the combination regimens.

6.1.9. Permitted Concomitant Therapy to be Used with Caution

Medication that are weak or moderate (as defined by the FDA; see the link in Appendix 3) inhibitors or inducers of CYP3A4/5 are not prohibited but should be administered with caution, as they may increase or decrease MS-553 exposure. (Moderate CYP3A inhibitors are prohibited in Cohort C.) Medications that are moderate inhibitors of CYP3A will require dose modifications as outlined in Section 5.2.5 for patients on the combination with acalabrutinib (Cohort B Series). Medications that are P-gp substrates must not be taken \leq 6 hours prior to venetoclax (Cohort C Series) as outlined in Section 5.2.3.

After Cycle 1, steroids at doses up to 20 mg prednisone or equivalent per day are allowed for symptomatic relief of lymphadenopathy and B symptoms, if needed.

After completion of Cycle 1, higher doses of steroids may be used for therapeutic treatment of GVHD or autoimmune cytopenia or other intercurrent illness after discussion with the medical monitor and/or Sponsor.

Systemic steroids (not inhalation or topical) in amounts of 20 mg or higher of prednisone or equivalent per day may be permitted under certain circumstances (e.g., as pre- and post-medication for reactions to contrast agents; treatment of pre-existing disease-related autoimmune cytopenia and hemolysis; those treated for GVHD; those with an acute need for a non-disease related condition (e.g., additional steroid requirement for adrenal insufficiency or other acute condition where a short course [up to 14 days] may be required). In such circumstances of non-disease-related conditions, please discuss with the medical monitor/Sponsor regarding continuation of dosing of study drug during this period of increased steroid administration.

6.1.10. Prohibited Concomitant Medications

Strong inhibitors or inducers of CYP3A4/5 and sensitive CYP3A4/5 substrates and compounds with known QT prolongation risk as listed in their package inserts or belong to drugs with known risk of Torsades de Pointers (TdP) on crediblemeds.org should be avoided whenever possible and should be discontinued at least 48 hours prior to initiation of study drug. Refer to Appendix 3 for examples of these medications. When substitution of another medication is not feasible, discussion with the medical monitor and Sponsor will be needed. For example, the metabolism of the drug in question may be more affected by other P450 enzymes and not CYP3A4 or CYP3A5, in such case use of that drug may be approvable for use in the study. If in doubt, please discuss with the medical monitor.

Medications that are known to cause or have the potential to cause QTc prolongation as listed in their package inserts or belong to drugs with known risk of Torsades de Pointers (TdP) on crediblemeds.org should be avoided whenever possible unless prior approval of the Sponsor or medical monitor is provided. Those with a history of increased risk for QT prolongation (e.g., congenital long QT-syndrome, low ventricular ejection fraction, impaired hepatic or renal function that could affect drug metabolism, uncorrected electrolyte disturbances, and history of drug-related prolonged QT interval) are addressed in Exclusion Criterion #13. When substitution of another medication has been approved by the Sponsor or medical monitor, patients taking medications known to cause QT/QTc prolongation as listed in as listed in their package inserts or belong to drugs with known risk of Torsades de Pointers (TdP) on crediblemeds.org should be monitored appropriately with serial ECGs. Refer to Section 5.2.5 for the prohibited concomitant medications.

